12.12. Expected Duration of Patient Participation

Patients will participate in the study for approximately 16 weeks, including screening and psychedelic preparation (up to 4 weeks), and ongoing AUD relapse prevention psychotherapy over 12 weeks.

12.13. Data Handling and Recordkeeping (Records Retention)

12.13.1. Inspection of Records

BPL or designee will be allowed to conduct site visits to the investigation facilities for the purpose of monitoring any aspect of the study. The Investigator agrees to allow the monitor to inspect the drug storage area, study drug stocks, drug accountability records, patient charts or records and study source documents, and other records related to study conduct.

12.13.2. Retention of Records

All correspondence related to this clinical study should be kept in appropriate study files. Records of patients, source documents, drug inventory, and REC and BPL or designee correspondence pertaining to the study must be kept on file. All study documents must be kept secured for a period of 2 years after a marketing application is approved for BPL-003, or 2 years after formal discontinuation of the clinical development of the investigational product or according to applicable regulatory requirements. There may be other circumstances in which BPL or designee is required to maintain study records; therefore, BPL or designee should be contacted before removing study records for any reason.

12.14. Publication Policy

A description of this clinical study will be available on <http://www.ClinicalTrials.gov> and other national registries of clinical studies, as required by local regulations.

It is anticipated that BPL will publish the results of this clinical study in medical/scientific journals and/or present the results in a variety of forums.

Publication by the clinical study site(s) of any data from this study must be carried out in accordance with the Clinical Study Agreement.

14. APPENDICES

APPENDIX 1: PROHIBITED CONCOMITANT MEDICATIONS WITH BPL-003

This list of medications is **not all-inclusive**; if necessary, please contact the Medical Monitor for any questions regarding a medication(s).

Except where specifically noted, the prohibited medications listed in the following table are prohibited from 1 week (or 5 half-lives, whichever is longer) prior to the administration of intranasal study medication until after the last dose of intranasal study medication.

Note in the following table: N, Prohibited; Y, Permitted, with restrictions (please refer to the column labeled "Comments" for additional guidance).

Drug Name or Class	Episodic Use (as needed)	Continuous Use	Comments	Reason for Prohibition
ADHD medications (e.g., atomoxetine, guanfacine)	N	N		Safety
Anorexiant (e.g., phentermine, phendimetrazine)	N	N		Safety
Anticholinesterase inhibitors	N	N		Subject population is excluded
Anticonvulsants	N	N	Subjects with seizures are excluded. Note: Anticonvulsants used for indications other than seizures may be allowed (eg, valproate for migraine)	Safety and PD interaction
Antidepressants	N	N		Safety and PD interaction
Antipsychotics	N	N		PD interaction

Drug Name or Class	Episodic Use (as needed)	Continuous Use	Comments	Reason for Prohibition
Benzodiazepines (at dosages equal to or less than the equivalent of 6 mg/day lorazepam) and non- benzodiazepine sleeping medication (including zolpidem, zaleplon, eszopiclone, and ramelteon)	Y	Y	Prohibited within 12 hours prior to the start of intranasal treatment session or cognition testing	Safety and PD interaction
Buspirone (Buspar)	N	N		PD interaction
Chloral hydrate, melatonin, valerian	N	N		Safety and PD interaction
Clonidine	N	N		Safety and PD interaction
Corticosteroids (systemic)	Y	N	Inhaled, intranasal, topical, and ophthalmic steroids are not prohibited. Intermittent IM/IV corticosteroids are permitted (chronic use prohibited)	PD interaction
Cough/cold preparations/nasal solutions containing vasoconstrictors, decongestants	Y	N	Intranasally administered decongestants (vasoconstrictors) should not be used from 1 hour prior to each intranasal study medication administration. Pseudoephedrine-containing oral products should not be used within 12 hours prior to an intranasal treatment session.	Safety and PD interaction
Dextromethorphan	N	N		PD interaction
Diphenhydramine	Y	N	Prohibited within 12 hours prior to the start of each intranasal treatment session	Safety

Drug Name or Class	Episodic Use (as needed)	Continuous Use	Comments	Reason for Prohibition
Ketanserin	N	N		Safety and PD interaction
Linezolid	N	N	Antibiotic with potential interaction	Safety and PK interaction
Lithium	N	N		PD interaction
Memantine	N	N		PD interaction
Methyldopa	N	N		Safety and PD interaction
Mirtazapine (Remeron)	N	N		
Monoamine oxidase-A (MAO-A) inhibitors	N	N	Examples are phenelzine (Nardil), isocarboxazid (Marplan), tranylcypromine (Parnate), moclobemide	Safety (possible risk of serotonin syndrome)
Monoamine oxidase-B (MAO-B) inhibitors	N	N	Examples are selegiline, rasagiline (Azilect)	Safety (possible risk of serotonin syndrome)
Opioids	N	N		PD interaction
Psychostimulants (e.g., amphetamines, methylphenidate, and modafinil, armodafinil)	N	N		Cardiovascular safety
Reserpine	N	N		PD interaction
Scopolamine	N	N		PD interaction

Drug Name or Class	Episodic Use (as needed)	Continuous Use	Comments	Reason for Prohibition
Serotonin agonists	N	N	Drugs that are known serotonin agonists are excluded. Examples are: naronapride, serotonin, vortioxetine, mosapride, urapidil, dihydroergotamine, cabergoline, ziprasidone, flibanserin, rotigotine, cinitapride, brexpiprazole, cariprazine, fenfluramine, pergolide, bromocriptine, lorcaserin, cisapride, metergoline, asenapine, renzapride, aripiprazole, prucalopride	
Triptans	Y	N	Can be taken except around time of dosing	
St. John's Wort	N	N		PD interaction and PK
Substances that work as MAOIs	N	N	BPL-003 is metabolized by MAO; therefore, these drugs are not allowed as concomitant medications and need to be discontinued. Examples are MOAI antidepressants.	PK
Trazodone (Desyrel)	N	N		PD interaction (blockade of 5-HT _{2A})

Abbreviations: 5-HT_{2A} = serotonin receptor 2A; IM = intramuscular; IV = intravenous; MAO = monoamine oxidase, MAOI = monoamine oxidase inhibitor; N = prohibited; PD = pharmacodynamic; PK = pharmacokinetic; Y = permitted (with restrictions; please refer to column labeled Comments for additional guidance).

APPENDIX 2: READINESS FOR DISCHARGE QUESTIONNAIRE – 5-MEO-DMT

Concept:

- Brief assessment scale (checkbox exercise) that will be utilized after dosing with 5-MeO-DMT
- Assessment will be performed every 30 min starting 90 minutes after dose
- Will determine when patients can safely leave the office, patient will need to remain until 4 hours post dose even if discharge confirmed safe before that time.

Assessment:

This questionnaire will assess the readiness of the patients to be discharged from the supervisory care after a 5-MeO-DMT treatment. The healthcare provider will assess several characteristics that indicated that the psychedelic effects of 5-MeO-DMT have subsided to a level where further monitoring is not necessary anymore.

Clinical Assessment (most sensitive feature first):

The assessment will be performed by a study clinician and initially, all the assessments will have to be performed at every time point but after the investigator acknowledges that an item is fulfilled this will no longer need to be asked each time but can be completed based on previously confirmed answer.

Each question must be answered with YES in order to be able to discharge the patient safely from care. Once all items are checked as a YES the last question to confirm that the patient is ready for discharge can be completed and no further reviews every 30 minutes are required. If this occurs before 4 hours post dose the patient will remain until the completion of 4 hours waiting period before actually being discharged. If the patient is not ready to be discharged at 4 hours post dose the every 30 minute assessments will stop but a final questionnaire will be completed once the Investigator is satisfied that the patient is ready prior to discharge.

- The patient is fully responsive, aware of their surroundings, and reacts adequately
- The acute psychedelic effects of the drug have completely subsided
- The patient is fully orientated (name, location, time)
- Blood pressure and pulse rate have returned to normal or only slightly elevated levels. The breathing frequency and body temperature are normal

- The patient has a stable gait and normal muscle coordination and can walk safely
- Potential side effects are mild to moderate in intensity and do not need to be medically monitored
- The patient has no acute suicidal ideations or suicidal intentions
- Possible distress or feelings of being overwhelmed have sufficiently subsided to a degree that the patient themselves feel safe to be discharged

After all prior assessments have been answered with YES the final question can be completed.
The last question cannot be ticked as yes until all the proceeding questions are yes.

- **In the opinion of the assessor, the patient is now safe to be discharged**

APPENDIX 3: FACTOR MEANS AND DESCRIPTIVE STATISTICS

Factor	Mean	Confid. -95.000%	Confid. +95.000%	Std.Dev.	Standard Error
COMP_SFR	2.622226	2.406279	2.838174	1.621456	.109568
XPCT_SFR	3.545983	3.382864	3.709103	1.224791	.082764
PURP_SFR	3.859695	3.618971	4.100419	1.807488	.122139
EMOT_SFR	3.754779	3.586491	3.923067	1.263598	.085386

Adapted from ([Singleton, 1999](#)).

APPENDIX 4: COGNITIVE BEHAVIOURAL RELAPSE PREVENTION INTERVENTION FOR ALCOHOL USE DISORDER

Patient cognitive behavioural relapse prevention intervention (RPI) will be conducted in line with manual devised by clinicians at Lambeth Addictions Consortium (centre) – a specialist community treatment clinic in the London Borough of Lambeth (operated by South London and Maudsley NHS Mental Health Foundation Trust). In the context of the centre’s integrated care pathway for moderate–severe AUD, patients will be invited to receive a structured RPI.

The RPI will align with UK national clinical recommendations ([National Institute for Health and Care Excellence 2011](#)) (NICE) for the community/outpatient treatment of adults with moderate and severe alcohol dependence who have successfully completed withdrawal using adaptations of cognitive behavioural therapies. NICE recognises the origins of effective treatment for AUD in Marlatt and Gordon’s model of relapse prevention ([Marlatt, 2005](#)) and Miller and Rollnick’s Motivational Interviewing ([Miller, 2002](#)), and the broad international evidence-base that has been summarised in meta-analytic systematic reviews since.

The study RPI will be adapted to integrate with the single session of BPL-003 with the aim of enhancing treatment engagement and effectiveness. It will include the following structural features:

- An empathic (therapeutic alliance building) and change focussed style of communication to encourage self-efficacy
- Linked case management for service users who have had difficulty engaging in treatment or are at risk of dropping out;
- An individualised care plan, developed in collaboration with the service user (and relevant others), that includes a comprehensive assessment of personal needs and goals, and required inter-agency working;
- Collaborative assessment (case formulation) to develop and update a working hypothesis of how alcohol-related problems have been maintained; how they are attenuated and prevented (including a focus on high-risk drinking situations, alcohol-related cognitions, behaviours, and evaluations);
- Modification of maladaptive alcohol-related and general cognitions and beliefs (including cognitive restructuring/reconsolidation, and behavioural experiments to develop coping skills);
- Interventions for common mental health conditions comorbid with AUD (including depression and anxiety, following NICE guidelines)
- Facilitated support to engage in recovery activities (including self-help groups);

During the study, the RPI will be offered to patients as weekly individual (in person and/or via video) sessions with a trained AUD therapist. Following immediately after screening and informed consent, with all sessions including coping strategies (and other homework assignments) to be deployed outside the clinic, the RPI will be structured across the following 3 phases:

Stage 1: Assessment and care planning (Weeks -2 to -1)

Session 1: This session will include a focused clinical history of the development of AUD, the objective will be to build rapport, discuss any previous experience of treatment, previous coping strategies, general expectations for alcohol treatment, social supports and stressors, symptoms of anxiety and depression, and set out treatment goals in the context of the care plan (90 minutes).

Session 2: The objective of this session will be to produce a collaborative testable hypothesis of how the disorder has been maintained. A micro-formulation will be based on recent typical (and unusual) episodes of alcohol use and will include contexts, triggers, physical sensations, elaborated cognition (attention, mental images, beliefs, appraisals, coping strategies, problematic affective and behavioural responses, post-drinking evaluations and problems (together forming vicious cycles of AUD maintenance) (90 minutes).

Stage 2: Early treatment (Weeks 1 to 4)

Sessions 3 to 6: The objective of initial sessions in this stage will be to use (and update) the AUD formulation to cognitively restructure elaborated cognitions, emotions and appraisals, and any unwanted/maladaptive behavioural responses. A basic behavioural activation approach will be used to review and identify mood increasing activities to reinforce recovery. Each session will review the participant's cognitive control over alcohol-related approach (craving) thoughts and decision making. This stage of treatment will aim to support the participant build and deploy cognitive control skills for lapse and relapse prevention.

Stage 3: Middle treatment (Weeks 5 to 8)

Sessions 7 to 10: Building on earlier sessions – and incorporating the experience of exposure to BPL-003 – micro-formulations of high-risk situations, learning examples of virtuous cycles where intrusive/elaborated approach cognitions for drinking have been successfully managed, and shifts/growth in personal values and appraisals, and interpersonal relationships and functioning. With an emphasis on creating, implementing, and reviewing behavioural experiments that test and modify expectations and beliefs. In this stage (approximately Session 6) will include a review of symptoms and the therapeutic process, care plan, and goal attainment, and encouragement to experience self-help and other recovery supports.

Stage 4: Later treatment and blueprint (Weeks 9 to 12)

Sessions 11 to 14: The aim of the final stage of the RPI will be to consolidate treatment, with a review of the participant's decision making and coping with high-risk situations and any lapses. The participant's general and micro-formulations (with the expectation of a transition from vicious to virtuous cycles of cognitions, appraisals, behaviours, and evaluations) will be incorporated with and shifts/growth in personal values and appraisals that flow from the RPI and BPL-003. The final session will focus on the evaluation of treatment goals (including a blueprint summary of the therapy), along with a discussion of further/ongoing needs and continuing care medical and welfare referral.

APPENDIX 5: REACTIVATION QUESTIONNAIRE

Re-Activations Questionnaire (ReAQ)

Epidemiological data and anecdotal reports indicate that the use of 5-MeO-DMT is associated with the potential occurrence of a complex and not well understood phenomenon that has been termed “reactivation” (Ortiz Bernal et al, 2022).

Anecdotal reports online do seem to suggest that reactivations tend to occur mainly at night as people are drifting off to sleep, and generally tend to dissipate the longer the time has elapsed from the time they took 5-MeO-DMT.

In a broad sense, it appears that reactivations are experienced as transient but intense (Type 1 Hallucinogen Persisting Perception Disorder (HPPD)) and tend to subside days or weeks after 5-MeO-DMT use in most cases, as opposed to persisting over longer periods of time as is the case with HPPD Type 2.

More data is needed, therefore the ReActivation Questionnaire (ReAQ) was developed for study teams to measure the occurrence, context and emotional valence of potential reactivations. The questionnaire will be completed by the investigator or study team.

1. Occurrence:

Since study drug dosing or last assessment of this scale (which ever occurred last), have you had a spontaneous re-experience or re-activation of a past study drug experience e.g., a flashback or a feeling as though your study drug experience is happening again?

- a. No (=> End of Assessment)
- b. Yes (=> Continue to questions below)

2. Frequency:

- a. When did the first re-experience or re-activation take place?

Instruction for the assessor: please write down date (DDMMMYYYY) and how many days after the dosing day they first occurred

- b. How many re-experience or re-activation events have you had in total i.e., since study drug dosing?

Instruction for the assessor: please write down the total number of events

3. **Emotional Valence:**

Were the re-experience or re-activation events mostly *negative, neutral, or positive* experiences?

Instruction for the assessor: please check the appropriate box

- *Mostly positive* ☐
- *Neutral* ☐
- *Mostly negative* ☐

4. **Functional Impact**

Please rate the impact of the reactivation symptoms on the following domains (None, Mild, Moderate, Severe).

Instruction for the assessor: please check the appropriate box for each domain (a, b and c)

	None	Mild	Moderate	Severe
a. Work				
b. Social Life				
c. Family Life				

5. **Narrative:**

Please provide more details on any re-activations or re-experiences e.g., how did they evolve, any comments on emotional valence?

Instruction for the assessor: please summarise the participant's narrative as free text (free text)

Ortiz Bernal, A. M., Raison, C. L., Lancelotta, R. L., & Davis, A. K. (2022, November 9). *Reactivations after 5-methoxy-N,N-dimethyltryptamine use in naturalistic settings: An initial exploratory analysis of the phenomenon's predictors and its emotional valence*. Frontiers. <https://doi.org/10.3389/fpsy.2022.1049643>

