3. STUDY ENDPOINTS

3.1. Primary Endpoints

Safety Endpoints

- Percentage of patients with treatment-emergent adverse events (TEAEs)
- Percentage of patients with clinically significant postdose abnormal laboratory tests
- Percentage of patients with clinically significant abnormal postdose vital sign measurements (HR, BP, and body temperature)
- Percentage of patients with postdose suicidal ideation as determined by the Columbia-Suicide Severity Rating Scale (C-SSRS)
- Change in C-SSRS score compared to Baseline at Days 7 and 84
- Readiness for discharge questionnaire
- Measure the frequency, emotional valence and functional impact of any re-activation events in the study through the Reactivation Questionnaire (ReAQ)

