4.2 Study endpoint(s)

4.2.1 Primary endpoint(s)

Safety Endpoints:

- Percentage of patients with treatment-emergent adverse events (TEAEs)
- Percentage of patients with clinically significant postdose abnormal laboratory tests
- Percentage of patients with clinically significant abnormal postdose vital sign measurements (Heart rate (HR), Blood Pressure (BP), and body temperature)
- Percentage of patients with postdose suicidal ideation as determined by the Columbia-Suicide Severity Rating Scale (C-SSRS)
- Change in C-SSRS score compared to Baseline at Days 7 and 84
- Readiness for discharge questionnaire
- Measure the frequency, emotional valence and functional impact of any re-activation events in the study through the Reactivation Questionnaire (ReAQ)

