14.8.7 Reactivation questionnaire (ReAQ)

ReAQ data will be listed. Occurrence (No/Yes), frequency (when the first re-activation took place, number of days after dosing day of first occurrence and number of re-experience or re-activation events in total after dosing), emotional valence (mostly positive, neutral and mostly negative), functional impact (none, mild, moderate and severe for domains; work, social life and family life) and narrative of potential reactivation will be summarised where applicable by treatment and timepoint.

15 Pharmacokinetic analyses

PK concentration data will be summarised using the PK concentration population.

Plasma concentrations of 5-MeO-DMT and its metabolites (bufotenine, 5-methoxyindolacetic acid (5-MIAA) and 5-MeO-DMT-N-Oxide) will be listed and summarised, by treatment, using descriptive statistics. Individual and mean plasma concentration–time profiles will be presented graphically.

For all variables, N (number of patients receiving the treatment in the population), n (number of observations), arithmetic mean, median, minimum, maximum, SD, %CV, and the 95% CI for the arithmetic mean will be provided.

The between-patient CV will be calculated using:

1. $\%CV_b = 100 * (SD/mean)$ with SD and mean of untransformed data

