Treatment	Planned Relative Time	451 – 480 msec		481 – 500 msec		> 500 msec		>30-60 msec Increase		>60 msec Increase	
		n	(%)	n	(%)	n	(%)	n	(%)	n	(%)
Treatment 1 (N=xx)	Time 1										
	Time 2										
	Time 3										

Source: Listing 16.2.xx

Programming notes: Continued with all time points. n = total number of results for that parameter

Template T_EG5

Table 14.3.7.xx Summary of clinically significant ECG values

Treatment	Planned Relative Time	Abnormal CS	
		n	(%)
Treatment 1 (N=xx)	Time 1		
	Time 2		

Source: Listing 16.2.xx

Programming notes: Continued with all timepoints. n = total number of results for that parameter
For cardiac telemetry, change planned relative time to Start and End date/time

Template T_RDQ

Table 14.3.7.xx Summary of readiness of discharge questionnaire (RDQ)- Time to discharge (units)

Treatment	Planned Relative Time	n	Mean	Median	Min	Max
Treatment 1 (N=xx)						

Source: Listing 16.2.xx

Programming notes: Continued with all time points

Template T_ReAQ_PG _

Table 14.3.8.xx Summary of re-activation questionnaire (ReAQ)

Assessment	Planned Relative Time	Treatment 1 (N=xx)
Number of Patients with Re-activation (%)	Time 1	Yes
		No
Number of Days after dose (Days)	Time 1	n
		Mean
		SD
		Median
		Min
		Max
Number of Re-activation events	Time 1	n
		Mean
		SD
		Median
		Min
		Max
Emotional Valence	Time 1	Mostly Positive
		Neutral
		Mostly Negative
Functional Impact- Work (%)	Time 1	None
		Mild
		Moderate
		Severe
Functional Impact- Social Life (%)	Time 2	
	Time 1	None
		Mild
		Moderate
		Severe
	Time 2	

Functional Impact- Family Life (%)	Time 1	None Mild Moderate Severe
<hr/>		

[figure not shown]
Source: Listing 16.2.xx

Programming notes: *Continued with all assessments and timepoints. Occurrence =Number of patients with Re-activation).*
Denominator for percentages will be total number of scores recorded (excluding N/A) at relative time point

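### The SAP's by-visit mean of ReAQ event counts averages a cumulative total over only the patients with a new event, so it can rise while new reactivations fall

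*Protocol*

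**What the plan says.** - **Endpoint.** Protocol 3.1 lists among the primary safety endpoints: "Measure the frequency, emotional valence and functional impact of any re-activation events in the study". SAP 4.2.1 repeats it.
- **Timing.** The Schedule of Events (Protocol Table 1) marks the ReAQ at Days 7, 28 and 84.
- **Item 1, occurrence (Protocol Appendix 5).** The window is the interval: "Since study drug dosing or last assessment of this scale (which ever occurred last), have you had a spontaneous re-experience or re-activation". The first answer option closes the form: "a. No (=> End of Assessment".
- **Item 2b, number of events (same appendix).** The window is the whole time since dosing: "How many re-experience or re-activation events have you had in total i.e., since study drug dosing".
- **Item 2a** asks for the date of the first event and how many days after dosing it fell.
- **SAP 14.8.7** keeps the cumulative variable, "number of re-experience or re-activation events in total after dosing", and summarises it by treatment and time point.
- **Shell T_ReAQ (SAP 19.2.1)** prints n, mean, SD, median, minimum and maximum for the number of events, and for days after dose, at each planned time. Its only denominator note concerns percentages: "Denominator for percentages will be total number of scores recorded (excluding N/A) at relative time point".
- **SAP 12.1** rules out imputing missing data. No SAP text scores a No as zero, carries a total forward or derives a count for an interval.

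**The concern.** The gate and the count use different windows. A patient whose reactivations have stopped answers No at the next visit, leaves no count there and drops out of the row. A patient whose reactivations continue stays in the row and reports the earlier events again. A patient's own total cannot fall, and the patients who remain are those with new events. Both features push the by-visit mean upward.

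The row carries part of the frequency component of a primary safety endpoint. If reactivations fade, a reader could take rising counts as a sign of persistence over 12 weeks, while the occurrence row a few lines above shows a decline. No footnote explains the disagreement.

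**Working it through.** The plan gives no figure for this point, so there is none to reproduce. The check applies its rules to constructed data. All event counts below are assumptions.

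**Rules applied.** At visit k, with x = new events in the interval:
- A patient enters the count row only if x > 0 (item 1 = Yes).
- The value entered is the sum of x from dosing to visit k (item 2b).
- A No contributes nothing (skip rule, no imputation).

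**Three patients.** A has 3 events by Day 7 and none after. B has 3 by Day 7 and 2 more by Day 28. C has none.

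| | Day 7 | Day 28 |
|---|---|---|
| Values in count row | 3, 3 | 5 |
| Planned n and mean | 2; (3+3)/2 = 3.0 | 1; 5/1 = 5.0 |
| New events | 3+3 = 6 | 2 |
| New events per assessed patient | 6/3 = 2.0 | 2/3 = 0.67 |
| Occurrence row (Yes) | 2/3 | 1/3 |

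The intervals differ in length (7 days, then 28 − 7 = 21 days). Per week, new events per patient are 2.0/1 = 2.0 and 0.67/3 = 0.22, so the fall is steeper still.

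**Twelve patients (the planned maximum).** New events in Days 0–7, 7–28 and 28–84: five patients (1,0,0), one (4,2,0), one (4,2,1), five (0,0,0).

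| | Day 7 | Day 28 | Day 84 |
|---|---|---|---|
| New events | 5+4+4 = 13 | 2+2 = 4 | 1 |
| Yes patients | 7/12 = 58.3% | 2/12 = 16.7% | 1/12 = 8.3% |
| Planned mean | 13/7 = 1.86 | (6+6)/2 = 6.00 | 7/1 = 7.00 |
| New events per assessed patient | 13/12 = 1.08 | 4/12 = 0.33 | 1/12 = 0.08 |

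The planned row is also wrong as a cumulative total. True total events are 13+4+1 = 18, a mean of 18/12 = 1.50 per patient. The Day 84 row would show 7.00 with n=1.

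**How often.** A simulation used 12 patients per trial, Poisson events with falling interval means (1/0.5/0.25, 2/1/0.5 or 1/0.3/0.1) and between-patient heterogeneity ranging from none to strong, with 8,000 trials per scenario. Among trials where new events fell and both visits had at least one Yes, the planned mean rose in 81–99% from Day 7 to Day 28 and in 77–99% from Day 7 to Day 84. These percentages depend on the assumed rates.

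**Days to first event.** If item 2a is read as first since dosing, a patient answering Yes at all three visits enters the same value three times. The patient with (4,2,1) would do so. Patients with only early events appear once. The by-visit summaries are therefore not separate pieces of information.

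**The case against.** The strongest reply is that the information needed is in the same output:

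- T_ReAQ opens with the number and percentage answering Yes or No at each visit. That row uses the interval window and includes the No patients.
- The count row prints its n, so the changing base is visible.
- Listing L_ReAQ gives each patient's occurrence, date, count, valence, impact and narrative. With up to 12 patients and no hypothesis, a reader can reconstruct what happened.

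All of this stands and limits the size of the problem. It does not make the count row correct.

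A second reply is that a total since dosing fits an endpoint about events in the study, and the SAP labels it as a total. This is fair as a reading of the endpoint. But such a total should be reported once, over everyone assessed. The planned row drops patients with only early events from the later visits, so it is not that total either.

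A third reply is that the SAP never restricts the row to Yes patients, and that a No could be treated as a structural zero rather than missing data. The restriction is indeed an inference from the skip rule plus no imputation. Plain zero-filling would not rescue the row, though: in the three-patient example Day 28 would become (0+5+0)/3 = 1.67. That is neither the new events per patient (0.67) nor the cumulative mean, (3+5+0)/3 = 2.67.

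Finally, the rise is not certain. A patient with late onset enters with a low total and pulls the mean down.

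**Conclusion.** The point holds for two rows of T_ReAQ: the number of events and, to a lesser degree, the days to first event. Followed as written, the plan can print a count that rises while new reactivations fall, and that contradicts the occurrence row of the same table. This rests on the skip rule, the cumulative wording of item 2b and the absence of any zero or carry-forward rule. The sizes shown rest on assumed event counts.

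Four stronger readings are not supported:
- A reader might infer that the whole endpoint misleads. It does not: the occurrence row shows the fall.
- A reader might infer that the plan double-counts events, for example 3+3+5 = 11 against a true 8. No SAP step adds counts across visits.
- A reader might infer that the trial sets out to test whether reactivations fade. Protocol 10.1.9 reports anecdotal suggestions of fading and says the ReAQ measures occurrence, context and emotional valence. It sets no aim about time course.
- A reader might infer that the mean must rise. It can, and often would under falling rates, but need not.

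Severity is modest, because the study is descriptive and small and individual data are listed. The correction is still worth making in a primary safety table.

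**What to change.** Change SAP 14.8.7 and T_ReAQ only. Replace the by-visit summary of item 2b with:

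1. **Total events per patient, reported once:** the latest recorded item 2b, or 0 if the answer was No at every completed visit, over all assessed patients.
2. **New events per interval:** item 2b minus the last recorded item 2b, 0 when item 1 is No, over all patients assessed at that visit. Show the interval length (about 7, 21 and 56 days). Flag any interval merged by a missed ReAQ; for example, missing Day 28 leaves one of about 84 − 7 = 77 days. If a recalled total is lower than an earlier one, list it and do not difference it.
3. **Days to first reactivation, once per patient:** from the earliest item 2a date.

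The occurrence row and the listing stay as they are. In the 12-patient example the new row would read 1.08, 0.33 and 0.08, with a single total of 1.50 per patient.

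The cost is a few lines of SAP text and one table shell, with no new data and no change to the questionnaire. The downside is slightly more derivation work and reliance on totals that patients recall.
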